8.2 Serious Adverse Event Procedures

8.2.1 Reference Safety Information

The reference for safety information for this study is the investigator's brochure which the sponsor has provided under separate cover to all investigators.

8.2.2 Reporting Procedures

All initial and follow-up SAE reports must be reported by the investigator to Quintiles Transnational Japan K.K within 24 hours of the first awareness of the event. Note: The 24-hour reporting requirement for SAEs does not apply to reports of abuse, misuse, overdose, or medication errors (see Section 8.1.7) unless they result in an SAE.

Shire	CONFIDENTIAL	Page 51
Protocol SHP633-302		27 Apr 2016

The investigator must complete, sign, and date the Shire Clinical Study Adverse Event Form for Serious Adverse Events (SAEs) and Non-serious AEs as Required by Protocol and verify the accuracy of the information recorded on the form with the corresponding source documents (Note: Source documents are not to be sent unless requested). The investigator must fax or e-mail the completed form to Quintiles Transnational Japan K.K. Applicable fax numbers and e-mail address can be found on the form (sent under separate cover).

8.2.3 Serious Adverse Event Definition

An SAE is any untoward medical occurrence (whether considered to be related to investigational product or not) that at any dose:

- Results in death
- Is life-threatening. Note: The term "life-threatening" in the definition of "serious" refers to an event in which the subject was at risk of death at the time of the event; it does not refer to an event which hypothetically might have caused death if it was more severe.
- Requires inpatient hospitalization or prolongation of existing hospitalization. Note: Hospitalizations, which are the result of elective or previously scheduled surgery for pre-existing conditions, which have not worsened after initiation of treatment, should not be classified as SAEs. For example, an admission for a previously scheduled ventral hernia repair would not be classified as an SAE; however, complication(s) resulting from a hospitalization for an elective or previously scheduled surgery that meet(s) serious criteria must be reported as SAE(s).
- Results in persistent or significant disability/incapacity
- Is a congenital abnormality/birth defect
- Is an important medical event. Note: Important medical events that may not result in death, be life-threatening, or require hospitalization may be considered an SAE when, based upon appropriate medical judgment, they may jeopardize the subject and may require medical or surgical intervention to prevent 1 of the outcomes listed in this definition. Examples of such medical events include allergic bronchospasm requiring intensive treatment in an emergency room or at home; blood dyscrasias or convulsions that do not result in inpatient hospitalization; or the development of drug dependency or drug abuse.

8.2.4 Serious Adverse Event Collection Time Frame

All SAEs (regardless of relationship to study) are collected from the time the informed consent/assent is signed until the defined follow-up period stated in Section 3.2 and must be reported to Quintiles Transnational Japan K.K within 24 hours of the first awareness of the event.

In addition, any SAE(s) considered "related" to the investigational product and discovered by the investigator at any interval after the study has completed must be reported to Quintiles Transnational Japan K.K within 24 hours of the first awareness of the event.

8.2.5 Serious Adverse Event Onset and Resolution Dates

The onset date of the SAE is defined as the date the event meets serious criteria. The resolution date is the date the event no longer meets serious criteria, the date the symptoms resolve, or the event is considered chronic. In the case of hospitalizations, the hospital admission and discharge dates are considered the onset and resolution dates, respectively.

In addition, any signs or symptoms experienced by the subject after signing the informed consent/assent form, or leading up to the onset date of the SAE, or following the resolution date of the SAE, must be recorded as an AE, if appropriate.

8.2.6 Fatal Outcome

Any SAE that results in the subject's death (ie, the SAE was noted as the primary cause of death) must have fatal checked as an outcome with the date of death recorded as the resolution date. For all other events ongoing at the time of death that did not contribute to the subject's death, the outcome should be considered not resolved, without a resolution date recorded.

For any SAE that results in the subject's death or any ongoing events at the time of death, unless another investigational product action was previously taken (eg, drug interrupted, reduced, withdrawn), the action taken with the investigational product should be recorded as "dose not changed" or "not applicable" (if the subject never received investigational product). The investigational product action of "withdrawn" should not be selected solely as a result of the subject's death.

8.2.7 Regulatory Agency, Institutional Review Board, Ethics Committee, and Site Reporting

Quintiles Transnational Japan K.K is responsible for notifying the relevant regulatory authorities/central institutional review boards (IRBs)/ethics committees (ECs) of related, unexpected SAEs. In addition the sponsor and/or designee is responsible for notifying active sites of all related, unexpected SAEs occurring during all interventional studies across the teduglutide program.

The investigator is responsible for notifying the local IRB or the relevant local regulatory authority of all SAEs that occur at his or her site as required.

8.3 Adverse Events of Special Interest

An AE of special interest is an AE (serious or nonserious) of scientific and medical concern specific to the sponsor's product or program and for which ongoing monitoring and immediate notification by the investigator to the sponsor is required.

The AEs of special interest that require expedited regulatory reporting for this study include the following:

- Growth of pre-existing polyps of the colon
- Benign neoplasia of the GI tract including the hepatobiliary system

• Tumor-promoting ability (eg, benign and/or malignant neoplasia of any kind, not limited to those of the GI or hepatobiliary system)

For AEs of special interest, Quintiles Transnational Japan K.K Quintiles Transnational Japan K.K must be informed within 24 hours of first awareness as per the SAE notification instructions described in Section 8.2.2 even if the event does not fulfill seriousness criterion.

8.4 Dose Interruption of Individual Subjects

The investigator is responsible for contacting the sponsor or designee when the subject's daily investigational product dosing regimen is interrupted. Attempts should be made to contact the sponsor or designee prior to dose interruption. Reasons for dosage interruption may include but are not limited to such as hospitalization and AEs, a lapse in investigational product delivery, etc.

Investigational product must be discontinued if any of the following events occur:

- Pregnancy
- Severe hypersensitivity, such as anaphylaxis determined by the investigator to be related to the investigational product. This does not include the presence of anti-teduglutide antibodies, mild injection site reactions or mild symptoms that according to the investigator do not pose a significant risk to the subject.
- An AE listed in Table 6 that is of NCI CTCAE severity Grade 3 or 4 and considered to be related to the investigational product administration (see Section 8.4.1)
- Confirmed drug-induced liver injury (DILI) related to teduglutide (see Section 8.4.2)

8.4.1 Dose Interruption Criteria Based on Known Risks of Teduglutide

The investigational product may be discontinued if the subject experiences an AE listed in Table 6 that is of severity \geq Grade 3 per the NCI CTCAE. All such AEs should be discussed with Shire's medical monitor or designee as soon as possible. Teduglutide administration must be discontinued if the AE is considered related to the investigational product. The length of dose interruption, and whether teduglutide administration resumes or is permanently discontinued, depends on the clinical situation.

Investigators and the DMC should be guided by the descriptions of Grade 3 and 4 events, as they relate to identified risks associated with the administration of teduglutide (see Table 6).

T.I.I. (4L - 4 N/ `	I	D 1	T 4 4
I Shie h	- A dvere	Se H vents i	that wav	Lega ta	IDAGA	Interruntion
			unai iviav .		DUSU.	

Adverse Event	Grade 3 Description	Grade 4 Description		
Gastrointestinal Disorders				

Adverse Event	Grade 3 Description	Grade 4 Description
Colorectal polyps	Severe or medically significant but not immediately life threatening; hospitalization or prolongation of existing hospitalization indicated; disabling; limiting self-care activities of daily living	Life-threatening consequences; urgen intervention indicated
Intestinal obstruction	Hospitalization indicated; elective operative intervention indicated; limiting self-care activities of daily living; disabling	Life-threatening consequences; urgen operative intervention indicated
Gallbladder and Bile Duct	Disease	6
Cholecystitis	Severe symptoms; radiologic, endoscopic or elective operative intervention indicated	Life-threatening consequences; urgent operative intervention indicated
Gallbladder perforation	Not Applicable	Life-threatening consequences; urgen intervention indicated
Gallbladder obstruction	Symptomatic and severely altered gastrointestinal function; tube feeding, total parenteral nutrition or hospitalization indicated; nonemergent operative intervention indicated	Life-threatening consequences; urgent operative intervention indicated
Gallbladder infection	Intravenous antibiotic, antifungal, or antiviral intervention indicated; radiologic, endoscopic, or operative intervention indicated	Life-threatening consequences; urgen intervention indicated
Alkaline phosphatase increased	>5.0 to 20.0x ULN	>20.0x ULN
Blood bilirubin increased	>3.0 to 10.0x ULN	>10.0x ULN
Bile duct stenosis	Severely altered gastrointestinal function; radiologic, endoscopic or elective operative intervention indicated	Life-threatening consequences; urgen operative intervention indicated
Pancreatic Disease		
Pancreatitis	Severe pain; vomiting; medical intervention indicated (eg, analgesia, nutritional support)	Life-threatening consequences; urgen intervention indicated
Pancreatic duct stenosis	Severely altered gastrointestinal function; tube feeding or hospitalization indicated; elective operative intervention indicated	Life-threatening consequences; urgent operative intervention indicated
Pancreas infection	Intravenous antibiotic, antifungal, or antiviral intervention indicated; radiologic or operative intervention indicated	Life-threatening consequences; urgen intervention indicated
Serum amylase increaseda	>2.0 to 5.0x ULN	>5.0x ULN
Lipase increaseda	>20 to 50x ULN	>5.0x ULN

Table 6 Adverse Events that May Lead to Dose Interruption

Adverse Event	Grade 3 Description	Grade 4 Description
Cardiovascular Disease		
Heart failure	Severe with symptoms at rest or with minimal activity or exertion; intervention indicated	Life-threatening consequences; urgent intervention indicated (eg, continuous intravenous therapy or mechanical hemodynamic support)

Table 6 Adverse Events that May Lead to Dose Interruption

Source: Common Terminology Criteria for Adverse Events, version 4.03, 14 June 2010

ULN=upper limit of normal

^a In the setting of clinically acute and symptomatic pancreatitis

8.4.2 Dose Interruption Criteria Based on Drug-induced Liver Injury

Teduglutide administration for an individual subject may need to be discontinued if the subject has clinical and laboratory evidence of potential DILI, in the absence of an alternative explanation, as identified by the following criteria:

- Subjects with normal (or low) values of ALT and AST at baseline:
 - ALT or AST >8x ULN
 - ALT or AST >5x ULN for more than 2 weeks
 - ALT or AST >3x ULN and (total bilirubin >2x ULN or INR>1.5)
 - ALT or AST >3x ULN with the appearance of fatigue, nausea, vomiting, right upper quadrant pain or tenderness, fever, rash, and/or eosinophilia (>5%)
- Subjects with baseline elevations of values of ALT and/or AST over ULN:
 - ALT or AST >8x ULN
 - ALT or AST >5x ULN and >2x baseline value for more than 2 weeks
 - (ALT or AST >3x ULN and >2x baseline value) and (total bilirubin >2x ULN or INR>1.5)
 - ALT or AST >3x ULN and >2x baseline value with the appearance of fatigue, nausea, vomiting, right upper quadrant pain or tenderness, fever, rash, and/or eosinophilia (>5%)

All laboratory values suggestive of potentially new DILI should be repeated and verified within 3 days. INR should be measured with this set of verification laboratory assessments and an inquiry should be made as to the presence of clinical symptoms consistent with new liver injury. The subject should be followed closely to determine the trajectory of the laboratory abnormalities and to evaluate the cause of liver injury. This evaluation may include, as clinically indicated, consideration of sepsis, acute viral hepatitis (eg, hepatitis A immunoglobulin M [IgM], hepatitis B surface antigen, hepatitis C antibodies, cytomegalovirus IgM, Epstein-Barr virus antibody panel), hepatobiliary obstruction (ultrasound), autoimmune hepatitis (anti-nuclear, anti-smooth muscle, anti-actin, or anti-liver kidney microsomal antibodies), intestinal failure

associated liver disease, cardiovascular causes such as ischemic hepatitis, and concomitant hepatotoxic treatments.

Additional evaluations may be performed at the discretion of the investigator in consultation with Shire medical monitor or designee.

Teduglutide administration must be discontinued if DILI is confirmed and deemed related to investigational product.

8.5 Early Termination of the Clinical Study

The DMC may recommend stopping the study if:

• At least 2 subjects develop the same event listed in Table 6 of severity CTCAE Grade 3

or

• 1 subject develops an event listed in Table 6 of severity CTCAE Grade 4 which is attributable to investigational product or is not reasonably related to the underlying disease process.

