9.4.1 Data Monitoring Committee

The DMC for this study will be conducted in accordance with the FDA Guidance for Clinical Trial Sponsors: Establishment and Operation of Clinical Trial Data Monitoring Committees (March 2006).

The DMC will be an external, independent board comprised of physicians with relevant training. The DMC will be restricted to individuals free of significant conflicts of interest, including, but not limited to, financial, scientific, or regulatory in nature. The DMC will be governed by a Charter agreed to by members of the Committee and the sponsor. Members of the Committee may not be study investigators or be employed at the same institution as a study investigator, individuals employed by Shire, independent contractors hired by Shire, or members of regulatory agencies. The DMC may make recommendations to Shire regarding stopping, modifying or continuing the study; however, Shire will have the final responsibility to determine whether the study should be modified or temporarily or permanently stopped.

Safety and tolerability results will be evaluated by a DMC which will convene approximately every 3 months during the active study period (date of the first subject's first dose to date of the last subject's last dose), based on subject enrollment. The DMC review will include all cumulative safety data from study assessment through the end of each review period.

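### The two-subject stopping criterion in Section 8.5 names Grade 3 only, so two children with the same disease-related Table 6 event at Grade 4 meet no listed criterion

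*Protocol*

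**What the plan says.** Protocol Section 8.5 opens with "The DMC may recommend stopping the study if" and gives two criteria joined by *or*.

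- **Criterion 1:** "At least 2 subjects develop the same event listed in Table 6 of severity CTCAE Grade 3". It sets no condition on cause and does not extend to higher grades.
- **Criterion 2:** one subject with a Table 6 event of Grade 4, provided that the event is "attributable to investigational product or is not reasonably related to the underlying disease process".

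Other text on the same table covers both grades. The mandatory discontinuation list in Section 8.4 includes "An AE listed in Table 6 that is of NCI CTCAE severity Grade 3 or 4" when the event is considered related to the product. Section 8.4.1 sets its threshold for possible discontinuation at Grade 3 and above, and adds "Investigators and the DMC should be guided by the descriptions of Grade 3 and 4 events". In Table 6 itself, the row "Gallbladder perforation" has no Grade 3 description (it is entered as not applicable), only a Grade 4 one.

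Section 9.4.1 gives the DMC a wider remit: "The DMC may make recommendations to Shire regarding stopping, modifying or continuing the study".

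**The concern.** Criterion 1 flags recurrence: the same known-risk event, at a serious grade, in more than one child. Taken at its word it counts Grade 3 cases only. A Grade 4 case can then enter only through criterion 2, which drops any event judged to belong to the underlying disease. The result is an inversion. Two disease-related Grade 3 cases meet a stopping criterion, while two disease-related cases of the same event at Grade 4, where Table 6 describes life-threatening consequences or the higher laboratory multiples, meet none.

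Disease attribution is plausible in this population. Section 1.1 names liver disease as a complication of long-term parenteral support. Section 8.4.2 lists intestinal failure associated liver disease and hepatobiliary obstruction among the causes to consider for liver injury. Table 6 includes raised bilirubin, raised alkaline phosphatase and intestinal obstruction. The guidance in Section 8.1.2 describes a related event as one that the subject's medical condition cannot explain. With about 5 children planned, two cases are 2/5 = 40% of the study.

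At stake is whether the only study-level stopping criteria listed in the protocol point the DMC in the right direction. No estimate or analysis is affected.

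**Working it through.** The plan gives no figure to reproduce here. The check treats Section 8.5 as two logical rules and applies them to every two-subject case.

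**Rules as written (Section 8.5)**

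- C1: the number of subjects with the same Table 6 event at Grade = 3 is at least 2.
- C2: at least one subject has a Table 6 event at Grade 4 that is attributable to product or not reasonably related to the disease.
- The criteria are met if C1 or C2 is true.

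**States.** Each subject's case is Grade 3 or 4, and is either D (judged disease-related) or P (attributable to product, or not reasonably disease-related). That makes 4 states, so 4 × 5 / 2 = 10 distinct pairs of subjects with the same event.

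| Pair | C1 as written | C2 | Met as written | Met if C1 is Grade ≥ 3 |
|---|---|---|---|---|
| 3D + 3D | yes | no | yes | yes |
| 3D + 3P | yes | no | yes | yes |
| 3P + 3P | yes | no | yes | yes |
| 3D + 4P | no | yes | yes | yes |
| 3P + 4P | no | yes | yes | yes |
| 4D + 4P | no | yes | yes | yes |
| 4P + 4P | no | yes | yes | yes |
| **3D + 4D** | no | no | **no** | yes |
| **3P + 4D** | no | no | **no** | yes |
| **4D + 4D** | no | no | **no** | yes |

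**Result**

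- All pairs: 7 of 10 qualify as written, and 10 of 10 with Grade 3 or higher.
- Both cases disease-related (3+3, 3+4, 4+4): 1 of 3 as written, the mildest, and 3 of 3 with the change.

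All three failing pairs contain a disease-related Grade 4 case.

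**Table 6 rows.** 2 gastrointestinal + 7 gallbladder and bile duct + 5 pancreatic + 1 cardiovascular = 15. One row, gallbladder perforation, has no Grade 3 level, so C1 as written can never be true for it.

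These are counts of combinations, not probabilities. The protocol gives no event rates, so no probability is attached to any of them.

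**The case against.** The strongest objection is that nothing operational depends on this wording. Section 8.5 says what the DMC may do and does not limit it to these grounds. Section 9.4.1 has the DMC review all cumulative safety data about every 3 months, with a general power to recommend stopping. Section 10.1.4 lets the sponsor suspend or terminate at any time for any reason. Section 8.4.1 already directs the DMC to both grades, and a committee of physicians would hardly treat the criterion as unmet because one case was worse. All of this stands and limits the consequence. It does not make the criterion right, because a listed threshold should not exclude the worse of two safety pictures.

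The gap is also narrow. Section 8.1.1 records a change in severity as a new event, so a child whose event passed through Grade 3 may still count. The gap therefore mainly concerns events first recorded at Grade 4. If any Grade 4 case is judged attributable or not disease-related, criterion 2 is met by that one subject, and this holds for gallbladder perforation too. These points also stand.

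It may be said that disease-related Grade 4 events are left out on purpose. That could explain criterion 2, which judges a single case. It cannot explain criterion 1, where disease-related Grade 3 cases count.

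Nor is it safe to assume that readers will supply the missing words. Section 8.5 sets Grade 3 and Grade 4 apart under different conditions, while Sections 8.4 and 8.4.1 spell out both grades where both are meant. The protocol of 18 December 2015 shows the same pattern in its Section 8.3: Grade 3 or higher for the individual subject, plain Grade 3 for the study.

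**Conclusion.** The point holds, as a minor defect in a stated safety criterion. Of the three grade pairs for the same disease-related Table 6 event in two children, only the mildest meets Section 8.5. The two-subject criterion is also unusable for 1 of the 15 Table 6 events. The intent was probably Grade 3 or higher, but the text does not say so.

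The conclusion rests on two things. The first is a literal reading of Grade 3 in criterion 1. The second is that Amendment 2 carries Section 8.5 over unchanged. The text examined is Amendment 1. The Amendment 2 contents list keeps Section 8.5 and its summary of changes lists nothing there, but the supplied Amendment 2 text ends before that section. Whether the two-subject criterion should also carry a causality condition is a clinical choice and is not questioned here.

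**What to change.** First confirm that Section 8.5 reads the same in Amendment 2. Then insert *or higher* after Grade 3 in the two-subject criterion, which matches the threshold used in Section 8.4.1. Check the corresponding line of the DMC charter, which was not available for this review, and align it if it repeats the current wording.

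The cost is two words in the protocol and at most one line in the charter. No endpoint, sample size, assessment or analysis changes.

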9 DATA MANAGEMENT AND STATISTICAL METHODS

9.1 Data Collection

The investigator or investigators' authorized site personnel must enter the information required by the protocol in the eCRF. A study monitor will visit each site in accordance with the monitoring plan and review the eCRF data against the source data for completeness and accuracy. Discrepancies between source data and data entered on the eCRF will be addressed by the investigator or qualified site personnel. When a data discrepancy warrants correction, the correction will be made by the investigator or authorized site personnel. The investigator must verify that all data entries in the eCRF are accurate and correct. Original diary data should be entered into the eCRF and take precedence over data collected over the phone. Data collection procedures will be discussed with the site at the site initiation visit and/or at the investigator's meeting. Once a subject is enrolled, it is expected that the investigator or authorized site personnel will complete the eCRF entry in a timely manner following the subject's visit.

